### **9.4.2 Clinical Laboratory Assessments**

For the laboratory assessments during OL safety period, the observed values and change from TC safety baseline values of the continuous hematology, coagulation and chemistry results will be summarized in SI units at each visit.

The number and percentage of subjects meeting at least 1 threshold analysis criterion event during the OL safety period will be summarized. The threshold analysis criteria are provided in Section 12.4.

Results of positive urine/serum pregnancy test from study 105 will be presented in individual subject data listings only. For positive serum pregnancy listing, subjects with serum HCG which are abnormally high will be selected. In addition, a listing containing individual subject hematology, chemistry, and coagulation values from study 105 will be provided. This listing will include data from both scheduled and unscheduled visits. The listings will be based on OL All Subjects set.

### **9.4.3 Electrocardiogram**

For the following ECG interval measurements during the OL safety period, a summary of observed values and change from TC safety baseline values will be provided at each visit (in msec): RR, PR, QT, and QT corrected for HR (QTcF), QRS duration, and HR (beats per minute).

The number and percentage of subjects meeting at least 1 threshold analysis criterion during the OL safety period will be summarized. The threshold analysis criteria are provided in Section 12.4.

### **9.4.4 Vital Signs**

For the vital signs measurements during the OL safety period, the observed values and change from TC safety baseline values will be summarized at each visit. The following vital signs parameters will be summarized: systolic and diastolic blood pressure (mm Hg), body temperature (°C), pulse rate (beats per minute), and respiratory rate (breaths per minute).

The number and percentage of subjects meeting at least 1 threshold analysis criterion during the OL safety period will be summarized. The threshold analysis criteria are provided in Section 12.4.

### **9.4.5 Pulse Oximetry**

[figure not shown]
For the percent of oxygen saturation measurements using pulse oximetry during the OL safety period, a summary of observed values and change from TC safety baseline values will be provided at each visit.

### **9.4.6 Physical Examination**

No tables/figures/listings will be provided for physical examination data.

### **9.4.7 Ophthalmology Examination**

Ophthalmology examination results for OL All Subjects Set will be provided in a data listing.

### 9.4.9 Summary of Safety Analysis

Safety assessments for each safety analysis set is presented in [Table 9-2](#).

Table 9-2 Summary of Safety Analysis

Analysis Set	Safety Assessment
OL-SS	
Routine safety:
 

• AEs, SAEs, Grade 3/4 AEs, AEs leading to discontinuation or interruption, related AEs and SAEs, overview (corresponding exposure adjusted rates)

• Clinical laboratory (Summary of change from TC safety baseline, TA)

• Vital signs (Summary of change from TC safety baseline, TA)

• ECG (Summary of change from TC safety baseline, TA)

• Pulse oximetry (Summary of change from TC safety baseline)

• Ophthalmology examination (listing)

## **10 Interim and DMC Analysis for Study 105**

### **10.1 Interim Analysis**

The protocol states that an IA for Study 105 may take place at any time during the study at the discretion of the sponsor to support regulatory and/or reimbursement dossiers. There is no plan to conduct IA for Study 105.

### **10.2 DMC Analysis**

An independent data monitoring committee (IDMC) was formed before initiation of study 105. The IDMC's objectives and operational details is described in the IDMC charter. The IDMC will conduct regular planned safety reviews of study data as outlined in the IDMC Charter and IDMC Analysis Plan.

## 12 APPENDICES

### 12.1 Analysis Visit Windows for Efficacy and Safety Assessments

Assessment	Visit	Target Study Day	Analysis Visit Window (in study days)
Serum Chemistry Hematology Vital Signs 	TC Safety baseline	--	Defined in Section 9.1
	OL Day 15	15	[1, 22] where day 1 is post-dose measurement
	OL Week 4	29	(22, 43]
	OL Week 8	57	(43, 85]
	OL Week 16	113	(85, 141]
	OL Week 24	169	(141, 211]
	OL Week 36	253	(211, 295]
	OL Week 48	337	(295, 379]
	OL Week 60	421	(379, 463]
	OL Week 72	505	(463, 547]
	OL Week 84	589	(547, 631]
	OL Week 96	673	(631, 687]
	OL Safety Follow-up	Not applicable	Use nominal visit
Standard 12-lead ECG	TC Safety baseline	--	Defined in Section 9.1
	OL Day 15	15	[1, 36] where day 1 is post-dose measurement
	OL Week 8	57	(36, 113]
	OL Week 24	169	(113, 253]
	OL Week 48	337	(253, 421]
	OL Week 72	505	(421, 589]
	OL Week 96	673	(589, 687]
	OL Safety Follow-up	Not applicable	Use nominal visit
Coagulation	TC Safety baseline	--	Defined in Section 9.1
	OL Week 24	169	[1, 253] where day 1 is post-dose measurement
	OL Week 48	337	(253, 421]
	OL Week 72	505	(421, 589]
	OL Week 96	673	(589, 687]
		OL Safety Follow-up	Not applicable

Assessment	Visit	Target Study Day	Analysis Visit Window (in study days)
Spirometry	Parent Study baseline	--	≤1 corresponding to the first dose date of parent study
	OL Day 15	15	(1, 22]
	OL Week 4	29	(22, 43]
	OL Week 8	57	(43, 85]
	OL Week 16	113	(85, 141]
	OL Week 24	169	(141, 211]
	OL Week 36	253	(211, 295]
	OL Week 48	337	(295, 379]
	OL Week 60	421	(379, 463]
	OL Week 72	505	(463, 547]
	OL Week 84	589	(547, 631]
OL Week 96	673	(631, 687]	
	OL Safety Follow-up	Not applicable	Use nominal visit
CFQ-R	Parent Study baseline	--	≤1 corresponding to the first dose date of parent study
	OL Week 4	29	(1, 43]
	OL Week 8	57	(43, 113]
	OL Week 24	169	(113, 253]
	OL Week 48	337	(253, 421]
	OL Week 72	505	(421, 589]
	OL Week 96	673	(589, 687]
	OL Safety Follow-up	Not applicable	Use nominal visit
Weight, Height and BMI (and the corresponding z-score) 	Parent Study baseline	--	≤1 corresponding to the first dose date of parent study
	OL Week 4	29	(1, 43]
	OL Week 8	57	(43, 85]
	OL Week 16	113	(85, 141]
	OL Week 24	169	(141, 211]
	OL Week 36	253	(211, 295]
	OL Week 48	337	(295, 379]
	OL Week 60	421	(379, 463]
	OL Week 72	505	(463, 547]
	OL Week 84	589	(547, 631]
	OL Week 96	673	(631, 687]
	OL Safety Follow-up	Not applicable	Use nominal visit
SwCl	Parent study baseline	--	≤1 corresponding to the first dose date of parent study
	OL Day 15	15	(1, 22]
	OL Week 4	29	(22, 43]
	OL Week 8	57	(43, 85]
	OL Week 16	113	(85, 141]
	OL Week 24	169	(141, 421]
	OL Week 96	673	(421, 687]

Notes:  
 Visit name for analysis purpose is used to report data in tables and figures.

**Table 12-1 Analysis Visit Windows for Efficacy and Safety Assessments in Study 105**

Assessment	Visit 	Target Study Day	Analysis Visit Window (in study days) 

 The analysis visit windows will be applied using the following rules for both scheduled and unscheduled visits:
 
 
1. If no numerical measurement is available within a visit window, the measurement will be considered missing for the visit.
 
2. If there is more than 1 numerical measurement available within a visit window, use the following rules:                             
 
i. The measurement closest to the target day will be used; or
 
ii. If there are multiple measurements with the same distance from the target day, the latest measurement will be used.
 
 
 
 
 For unscheduled vital signs measurements collected at Study Day 1, if any, they will be treated as post-dose observations.
 
 Weight will also be used in the threshold analysis in which the TC safety baseline will be used to calculate change.
			

Derived Variables:
 
 
1. Age (in years) at first dose date and post-baseline visit (for demographics, listing and the calculation of [percent] predicted spirometry variables):                             
Obtain the age at informed consent in “yy, mm” format (e.g., 24 years, 6 months) in parent study from the Vital Signs (VS) page at the Screening Visit in parent study, and add 0.5 month to convert to days.
 
Obtain the informed consent date.
 
Then age (in years) at first dose or post-baseline visit = [(first dose date or post-baseline visit date – informed consent date in parent study) in days + age at informed consent (in days) in parent study]/365.25.
 
 
2. Age (in months) at first dose date and post-baseline visit (for use in calculation of BMI and weight z-score):                             
Obtain the age at informed consent in “yy, mm” format (e.g., 24 years, 6 months) in parent study from the VS page at the Screening Visit in the parent study.
 
Obtain the informed consent date.
 
Then age (in months) at first dose or post-baseline visit = integer part of {(age at informed consent (in months) in parent study + 0.5 + diff(first dose date or post-baseline visit date, informed consent date) in months in parent study)} + 0.5.
 
 
3. Missing first dose date or last dose date                             
If the last dose date is missing or partial date is reported, the last dose date will be imputed based on, in descending order priority, the Early Treatment Termination (ETT) visit date, last visit date before the Safety Follow-up, or the last study drug administration date from EX SDTM domain, as appropriate. The imputation algorithm will ensure the imputed last dose date does not exceed the study participation end date.
 
 
4. Electrocardiogram:                             
TC safety Baseline is defined in Section 9.1. If multiple ECG measurements are obtained on the same calendar day during the analysis period,
 
 
○ For summary purpose, the average value will be used as the ECG on that day;
 
○ For threshold analysis purpose, all ECG values will be used
 
 
 
			

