9.1.1 Treatment Period

Treatment Period assessments are listed in [Table 3-1](#).

The ICF and, when appropriate, assent form, can be signed up to 28 days prior to Day 1. After obtaining informed consent and confirming eligibility, subjects will receive the first dose of study drug on Day 1. Administration details are provided in Section 9.6.

The Day 1 Visit of this study will be on the **same day** as the last scheduled visit of the parent study. Subjects will NOT have to repeat any Day 1 assessments that were specified to be performed at the last scheduled visit in the parent study.

Subjects who were enrolled and remained clinically stable but had Day 1 study drug administration procedures delayed by no more than 7 days for reasons not related to their clinical status will have to repeat the safety (Section 11.7) and spirometry (Section 11.6.1) assessments that were specified to be performed at the Day 1 Visit before receiving their first dose of study drug.

Subjects who have not received the first dose of study drug within 7 days of the last dose of study drug in the parent study, or subjects who had Day 1 study drug administration procedures delayed by no more than 7 days for a reason related to clinical status, will have to repeat all Day 1 assessments.

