11.7.3 Physical Examinations and Vital Signs

A PE of all body systems and vital signs assessment will be performed at the select study visits (see Table 3-1). At other visits, symptom-directed PEs and symptom-directed vital sign assessments will occur at any time if deemed necessary by the investigator or healthcare provider.

A complete PE includes a review of the following systems: head, neck, and thyroid; eyes, ears, nose, and throat (EENT); respiratory; cardiovascular; lymph nodes; abdomen; skin; musculoskeletal; and neurological. Breast, anorectal, and genital examinations will be performed when medically indicated. Any clinically significant abnormal findings in PEs will be reported as AEs.

Vital signs include blood pressure (systolic and diastolic), temperature (oral), pulse rate, and respiration rate. These will be assessed before dosing and following at least a 5-minute rest.

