#### **Baseline value:**

- The parent study baseline is defined as the most recent non-missing measurement (scheduled or unscheduled) collected before the first dose of study drug in the parent study (studies 102 or 103). The parent study baseline will be used to calculate the absolute and relative change from baseline for efficacy analyses unless otherwise specified.
- The TC safety baseline is defined as the most recent non-missing measurement (scheduled or unscheduled) collected before the first dose of study drug in the parent study (if the subject actually received at least one dose of VX-659/TEZ/IVA during the parent study) or the first dose of study drug in the OLS (if the subject did not actually receive at least one dose of VX-659/TEZ/IVA during the parent study). The TC safety baseline will be used in the safety analyses.

**Change (absolute change)** from baseline will be calculated as post-baseline value - baseline value.

**Unscheduled visits:** Unscheduled visit measurements will be included in analysis as follows:

- 1) In scheduled visit windows per specified visit windowing rules
- 2) In the derivation of baseline and last on-treatment measurements
- 3) In the derivation of maximum and minimum values, and maximum and minimum change from baseline values during the analysis period for the safety analyses
- 4) In individual subject data listings as appropriate

**Visit windowing rules:** The analysis visit windows for protocol-defined visits for study 105 are provided in Section 12.1. The visit window for the parent studies are described in the SAP for the individual parent studies.

**Incomplete/missing data** will not be imputed, unless specified otherwise.

**Outliers:** No formal statistical analyses will be performed to detect or remedy the presence of statistical outliers, unless specified otherwise.

**Multiplicity:** There will be no multiplicity adjustment, unless specified otherwise.

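### SAP Table 12-1 note 3 calls every unscheduled Day 1 vital sign post-dose whatever its time, which conflicts with the TC safety baseline in SAP 9.1 for subjects new to the triple combination

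*SAP*

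**What the plan says.** **Baseline rule (SAP 9.1).** "The TC safety baseline is defined as the most recent non-missing measurement (scheduled or unscheduled) collected before the first dose of study drug". The anchor is the first parent-study dose for subjects who took TC there. It is the first open-label dose "if the subject did not actually receive at least one dose of VX-659/TEZ/IVA during the parent study", which means the placebo and TEZ/IVA arms. The list of uses for unscheduled measurements includes "In the derivation of baseline and last on-treatment measurements", and also the maxima, minima and extreme changes in the safety analyses.

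**Appendix rule (SAP Table 12-1, note 3).** "For unscheduled vital signs measurements collected at Study Day 1, if any, they will be treated as post-dose observations". The note is attached to vital signs only. In the same table row, the first on-treatment window (OL Day 15) covers study days 1 to 22 and carries the words "1, 22] where day 1 is post-dose measurement".

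**Protocol.** Section 11.7.3 says of vital signs: "These will be assessed before dosing and following at least a 5-minute rest". Section 9.1.1 covers subjects whose Day 1 dosing is delayed. Some must repeat the safety and spirometry "assessments that were specified to be performed at the Day 1 Visit before receiving their first dose of study drug", and others must repeat all Day 1 assessments.

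**The concern.** SAP 9.1 decides whether a value is baseline by whether it came before the first dose. Note 3 decides by whether it was scheduled. The two agree for an unscheduled Day 1 reading taken after dosing and disagree for one taken before it.

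The SAP gives no reason for the exception. Serum chemistry and hematology share the row without the note, and the ECG and coagulation rows use the same Day 1 wording without it. That wording already presumes that Day 1 values can be split into pre-dose and post-dose.

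Vital signs are part of the primary endpoint. SAP 9.4.4 counts subjects who meet a threshold criterion at least once in the open-label safety period, so a single misplaced reading can matter. It can matter twice: as a false on-treatment value, and through the baseline against which later readings are judged.

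**Working it through.** The plan gives no figure on this point, and its sample-size statements do not depend on it. The check traces the rule through the text and then sizes it under stated assumptions. Study Day 1 is taken to be the date of the first open-label dose.

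**1. Who is affected.** Subjects who took TC in the parent study keep a parent-study baseline, so note 3 cannot change it. The baseline conflict is confined to TC-naive subjects with an unscheduled Day 1 reading that was truly pre-dose.

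**2. How such a reading could arise.** One route is an ordinary pre-dose recheck. Another is a repeat required by Protocol 9.1.1 after delayed dosing, if it falls on the dosing day and is recorded as unscheduled. The documents do not say how those repeats are recorded. If they were recorded that way, the value left as baseline could come from the last parent-study visit, days earlier.

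**3. Visit summaries.** The value closest to the target day is used. Day 1 is 15 − 1 = 14 days from target, and an on-time Day 15 visit is at most 3 days away. The furthest other days in the window are Day 2 (13 days) and Day 22 (7 days). A Day 1 reading is therefore used only if nothing else lies in the window, and means hardly move.

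**4. Threshold counts, by constructed example (systolic, mmHg).**

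- First pre-dose reading 150, pre-dose repeat 132. Under SAP 9.1 baseline is 132. Under note 3 it is 150, and the 132 counts as an on-treatment fall of 18, which meets the criterion for a decrease above 10. A later true value of 148 is a rise of 16 under SAP 9.1 but a fall of 2 under note 3, so a real increase is hidden.
- First pre-dose reading 118, pre-dose repeat 134. Under note 3 baseline is 118, and the 134 counts as an on-treatment rise of 16. A later 120 is a fall of 14 under SAP 9.1 but a rise of 2 under note 3, so a real decrease is hidden.

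The error can go either way.

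**5. Chance that one misplaced reading crosses a change threshold with no drug effect.** For two independent pre-dose readings with within-subject SD s (assumed; not in the documents), P = 1 − Φ(threshold / (s√2)). By symmetry the same values apply to falls.

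| s (mmHg) | Systolic rise above 10 | Systolic rise above 20 |
|---|---|---|
| 4 | 3.9% | 0.02% |
| 6 | 11.9% | 0.9% |
| 8 | 18.8% | 3.9% |
| 10 | 24.0% | 7.9% |

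For the diastolic criterion of a rise above 5 mmHg, P is 27.8% at s = 6 and 32.9% at s = 8.

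**6. Possible numbers.** Assume 200 of 400 subjects are TC-naive, 1% to 10% of them have an unscheduled Day 1 reading, and 25% to 100% of those readings are pre-dose.

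- Misclassified subjects: 200 × 0.01 × 0.25 = 0.5, up to 200 × 0.10 × 1 = 20.
- False systolic rises above 10 mmHg: 0.5 × 0.119 = 0.06 (s = 6), up to 20 × 0.188 = 3.8 (s = 8), which is under 1% of 400.
- False diastolic rises above 5 mmHg: 0.5 × 0.278 = 0.14, up to 20 × 0.329 = 6.6.

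Fewer subjects would be added to each count, because a subject who meets the criterion later anyway is counted once. The baseline shift in step 4 is a separate effect that these figures do not include.

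**The case against.** The strongest reply is that note 3 is a sensible conservative default. The scheduled Day 1 reading is pre-dose, so an extra reading that day may well come after dosing, for instance because the subject felt unwell. The default also fits the SAP's other safety conventions: adverse events with unclear start dates become treatment-emergent, and missing relationship counts as related. This stands for readings of unknown time. It does not justify overriding a time that is known.

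A reader might infer from Protocol 11.7.3 that unscheduled Day 1 readings are pre-dose. The documents do not support that. The before-dosing rule is written for vital signs at visits in the schedule, and the same section allows symptom-directed readings at any time at other visits.

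A reader might also infer that the rule selectively pushes abnormal pre-treatment readings into the on-treatment counts. That does not follow. After a high first reading, the abnormal value is the scheduled one; note 3 leaves it as baseline and moves only the repeat. A high baseline makes rises harder to meet and falls easier. No single direction of bias can be claimed.

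Feasibility is a fair objection. Protocol 9.6.1 asks for dose times only around the Week 4 pharmacokinetic sample, and no section says that clock times are captured for Day 1 doses or vital signs. Leaving untimed readings out of the threshold counts could discard genuine abnormalities after the first dose, so the remedy should not do that.

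Finally, the safety analysis is descriptive and without testing, so no formal inference is at risk.

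**Conclusion.** The conflict between note 3 and SAP 9.1 is certain from the text. For a TC-naive subject with an unscheduled reading truly taken before the first open-label dose, note 3 gives the wrong baseline and puts a pre-treatment value into the on-treatment extremes and threshold analysis.

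Whether any such readings exist is not known; the note itself allows for none. Not every misclassified subject would have a false event, because the reading must cross a Table 12-6 threshold or be an extreme value. The range of 0.5 to 20 subjects, and of about 0.1 to 3.8 false systolic rises above 10 mmHg, rests wholly on assumed shares and SDs and assumes independent readings. A recheck prompted by an abnormal first value would behave differently. The effect is probably small, and visit means are almost untouched. Severity: minor.

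**What to change.** Amend note 3 as follows:

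- Classify unscheduled Day 1 vital signs by recorded time, or by a recorded pre-dose/post-dose flag, against the first open-label dose.
- Treat the Day 1 repeats that Protocol 9.1.1 requires before dosing as pre-dose, however they are recorded.
- Keep post-dose as the default only for other readings with no usable time, and flag those in the listing.

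The baseline then follows SAP 9.1, and possible post-dose abnormalities stay in the threshold counts. The cost is one revised note and a small programming change. The limitation is that some untimed readings still rest on a default.

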## 12.2 Imputation Rules for Missing Prior/Concomitant Medication Dates

Imputation rules for missing or partial medication start/stop dates in study 105 database are defined below:

1. Missing or partial medication start date:
  - a. If only DAY is missing, use the first day of the month.
  - b. If DAY and Month are both missing, use the first day of the year.
  - c. If DAY, Month and Year are all missing, use a date before the first dose date (for programming purpose use Jan. 01, 2000 to impute).
2. Missing or partial medication stop date:
  - a. If only DAY is missing, use the last day of the month.
  - b. If DAY and Month are both missing, use the last day of the year.
  - c. If DAY, Month and year are all missing, assign ‘continuing’ status to stop date (for programming purpose use Dec. 31, 2050 to impute).

In summary, the prior, concomitant, or post categorization of a medication is described below.

**Table 12-2 Prior, Concomitant, and Post Categorization of a Medication**

Medication Start Date	Medication Stop Date		
	< First Dose Date of Study Drug	≥ First Dose Date and ≤ End Date of TE Period	> End Date of TE Period
< First dose date of study drug	P	PC	PCA
≥ First dose date and ≤ End date of TE period	-	C	CA
> End date of TE period	-	-	A

P: Prior; C: Concomitant; A: Post

Same imputation rule will be implemented for missing and/or partial dates of non-pharmacological treatment/procedure.

